Rationale:	There is a paucity of treatment options for subjects with resistant AML. Recently AML has been shown to be a multi-genetic disease with sub-clonal architecture that evolves spontaneously and in response to treatment. Chemotherapy-resistant leukemic clones can quickly gain dominance by “survival of the fittest” dynamics. One way of targeting minor yet resistant clones is to augment the effectiveness of current chemotherapy drugs. Hromas et al. discovered the importance of the Metnase complex in repairing chemotherapy related DNA damage in leukemia and other cancers (1-3). Screening studies identified ciprofloxacin as a Metnase inhibitor that chemosensitizes leukemic myeloblasts to etoposide chemotherapy (4). The non-overlapping toxicity profiles of ciprofloxacin and etoposide, and their additive effectiveness in this model, make these agents attractive candidates for use in combination in subjects with resistant AML.
Primary Objective:	
In subjects with resistant AML, to
 
 Phase 1b: Establish the maximum tolerated dose (MTD) of oral ciprofloxacin when given in combination with a fixed dose of oral etoposide to subjects with resistant AML. Phase II: Determine the complete response (CR, CRi, and CRp, see Appendix A) rate to treatment with ciprofloxacin and etoposide at the MTD in adults with resistant AML.
Secondary Objectives:	
In subjects with resistant AML, to
 
 Determine the safety and feasibility of treatment with oral ciprofloxacin and etoposide; Measure duration of complete response, of progression free survival and of overall survival following treatment with oral ciprofloxacin and etoposide; and Estimate the incidence of Grade ≥ 3 adverse events following treatment with ciprofloxacin and etoposide.
Study Design:	This is an open-label, single arm, Phase Ib/II study of oral ciprofloxacin and etoposide in subjects with resistant AML. This study is designed to evaluate the complete response rate, the safety profile, and biologic activity of the combination of oral ciprofloxacin and etoposide in subjects with resistant AML. For both study phases, all subjects will receive 1 cycle of induction. At the end of Cycle 1, subjects who demonstrate progressive disease will have completed study treatment. For any subject who demonstrates stable disease or a

partial response, a second cycle of induction will be given. No subject will receive more than 2 cycles of induction.

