Safety Assessments:	
Subjects will be evaluated weekly during and for at least 28 days following the last cycle of chemotherapy. Assessments will include (See Table 1):
 
 • Interval history, review of systems, medications, new allergies, and physical examination with vital sign measurements; • Weekly laboratory assessments, including a CBC with differential and CMP; and • Toxicity assessment per the NIH Common Toxicity Criteria Adverse Event (CTCAE) version 4.
Efficacy Assessments:	
Efficacy parameters used to assess response include hemoglobin, ANC, platelet count, circulating blasts, and bone marrow aspirate and/or biopsy.

Sample Size Estimation	
In prior clinical trials of oral etoposide in resistant AML the CR rate has been approximately 20%. It is expect that the combination of etoposide with ciprofloxacin will improve CR to 40%. In order to detect this difference with type I error rate of 0.10 and power of 80%, when the true response rate is 40%, a minimum of 24 evaluable subjects will be treated in Phase II based on the Simon’s two-stage MiniMax design. Accounting for 15-20% drop out rate, a total of 30 subjects will need to be recruited to this phase.

Table 1. Study Events Schedule

Assessment	Screen (≤ 21 days prior to Day 1)	Cycle 1					Cycle 2		End of Treat- ment ¹² ± 7days	Long- Term Follow Up ¹³
		Day 1	Day 8±2	Day 15±2	Day 22±2	Day 28±2	Days 1, 8, 15, 22±2	Day 28±2		
Signed Informed Consent	X									
Demographics	X									
Medical /Treatment History	X									
Medication History ¹	X	X	X	X	X	X	X	X	X	
Interval History/Physical Examination	X	X	X	X	X	X	X	X	X	
Toxicity Assessment		X	X	X	X	X	X	X	X	
Review of Systems		X	X	X	X	X	X	X	X	
Weight	X	X	X	X	X	X	X	X	X	
ECOG Performance Status	X	X	X	X	X	X	X	X	X	
12-lead electrocardiogram (ECG) ²	X		X			X			X	
Vital Signs ³	X	X	X	X	X	X	X	X	X	
Hematology Laboratory Evaluations ⁴	X	X	X	X	X	X	X	X	X	
Blood Chemistry Laboratory Evaluations ⁵	X	X	X	X	X	X	X	X	X	
Serum Pregnancy Test (females) ⁶	X					X		X	X	
Administer Ciprofloxacin ⁷		X	X				X			
Administer Etoposide ⁸			X				X			
Bone Marrow Aspirate and/or Biopsy ⁹	X					X		X	X	
Adverse Events Assessments ¹¹	X	X	X	X	X	X ¹³	X	X	X	
Survival Assessment										X

¹ Document all medications taken during the two (2) weeks prior to screening and throughout and for 28 days after last treatment.

² Includes: rhythm, rate, and PR, QRS, and QTc intervals.

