³ Includes: systolic and diastolic blood pressure, pulse rate, respiratory rate, and temperature.

⁴ Complete CBC including: hemoglobin, hematocrit, platelet and white blood cell count (WBC) with differential including circulating blasts and absolute neutrophil count.

⁵ BUN, creatinine, uric acid, total bilirubin, AST, ALT, alkaline phosphatase, LDH, sodium, potassium, calcium, magnesium, phosphorous, bicarbonate, chloride, glucose, albumin, and total protein.

⁶ Serum pregnancy test within 1 week of Cycle 1 Day 1 for females of childbearing potential. Repeat within one week prior to first day of each subsequent cycle.

⁷ Ciprofloxacin will be administered orally twice daily on Days 1 to 10 of a 28-day cycle.

⁸ Etoposide 200 mg will be administered orally once daily on Days 2 to 8 of a 28-day cycle.

⁹ The screening bone marrow assessment must be performed within 42 days of Cycle 1 Day 1 and must be reviewed at UF. If bone marrow analysis results from outside lab is used to confirm diagnosis, slides must be made available to be read by UF pathologist. This must confirm a diagnosis of AML, non-M3. In case of archived marrow used for eligibility or bone marrow inaspirable or slides unavailable to be read by UF pathologist, and there is greater than 10% blast present, peripheral blood may be collected for flow cytometry.

¹¹ Monitoring for SAEs and AEs starts the day patient signs the informed consent form (ICF), continuing throughout the study. Subjects who have received at least one dose of study drug and discontinue prematurely (regardless of reason) will be followed for any adverse events that occur during the study until 28 days (± 2 days) following the last dose of study treatment (i.e., the Follow-up Visit).

¹² End of treatment visit will occur at CID28 visit in subjects with progressive disease or at study withdrawal if the date does not correspond to a protocol-specified visit. Additional follow-up will include an assessment for the evaluation of AEs and concomitant medications 28 days (± 7 days) after the last dose of study medication. Other assessments will be performed as necessary by the treating physician.

¹³ All subjects will be followed monthly until: disease progression, death, or until 3 years from the on-study date.

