7.1.2 Efficacy Data

The efficacy outcomes of interest will be CR (including CRi and CRp) as defined in [Appendix A](#). The efficacy variables, which will be used to assess response, include hemoglobin, ANC, platelets, circulating blasts, bone marrow aspirate and biopsy.

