14.1 Appendix A: AML Response Criteria According to IWG

Response Criterion	Neutrophils (μL)	Platelets (μL)	Bone Marrow Blasts (%)	Other
CR	>1,000	>100,000	<5	Transfusion independent, no evidence of EMD
CRi (CR with incomplete blood counts)	<1,000	<100,000	<5	No evidence of EMD
CRp (CR with incomplete platelet recovery)	>1,000	<100,000	<5	No evidence of EMD
Disease Progression			> 25% increase from baseline	

Key: AML=acute myelogenous leukemia; CR=complete remission; EMD=extramedullary disease; IWG=International Working Group;

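### Circulating blasts are named as a response variable, but Appendix A gives them no role in scoring CR, CRi or CRp

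*Combined protocol and SAP*

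**What the plan says.** Section 7.1.2 ties the efficacy outcome to one table: "The efficacy outcomes of interest will be CR (including CRi and CRp) as defined in" Appendix A. Its next sentence reads: "The efficacy variables, which will be used to assess response, include hemoglobin, ANC, platelets, circulating blasts, bone marrow aspirate and biopsy". The synopsis, under Efficacy Assessments, says much the same: "Efficacy parameters used to assess response include hemoglobin, ANC, platelet count, circulating blasts, and bone marrow aspirate and/or biopsy". The data are there, because the hematology footnote to Table 1 specifies "white blood cell count (WBC) with differential including circulating blasts and absolute neutrophil count" and a CBC is scheduled at every visit through end of treatment.

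Appendix A sets these conditions:

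| Row | Neutrophils (/µL) | Platelets (/µL) | Marrow blasts | Other |
|---|---|---|---|---|
| CR | >1,000 | >100,000 | <5% | "Transfusion independent, no evidence of EMD" |
| CRi | <1,000 | <100,000 | <5% | no EMD |
| CRp | >1,000 | <100,000 | <5% | no EMD |

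No row mentions blasts in the blood. Section 11.1 applies the Simon two-stage rules to the response rate and points to Appendix A: stop with 2 or fewer responders in 14, reject the 20% null with 8 or more in 24.

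**The concern.** The protocol says it uses a variable to judge response, and then the table that defines response does not use it. Suppose a subject has 4% marrow blasts, no extramedullary disease, counts that fit one of the rows, and leukemic blasts on the differential. That subject meets the row as written. An assessor who gives weight to section 7.1.2 could decline to call it a response; one who applies Appendix A literally would call it one. Both could claim to follow the protocol.

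The trial is open-label and single-arm, and the documents describe no independent review of response, so nothing downstream would resolve such a disagreement. The Phase II decisions turn on single subjects (2 versus 3 of 14, 7 versus 8 of 24). Duration of complete response, a secondary objective, inherits the same ambiguity.

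**Working it through.** **1. Is there a rule elsewhere?** Section 7.1.2, the synopsis, the visit schedules in section 6.2, section 7.2.4 and Appendix A were compared. Circulating blasts are collected throughout and named twice as a response variable. No section gives a threshold or says what a positive finding does to the response category. Absence of extramedullary disease does not fill the gap, since nothing in the documents defines EMD to include blasts in the blood.

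**2. Reproduce the plan's design.** Inputs from section 11.1: null rate 0.20, alternative 0.40, type I error 0.10 (taken as one-sided), power 80%, stop if ≤2 of 14, reject if ≥8 of 24. With X₁ ~ Bin(14, p) and X₂ ~ Bin(10, p):

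- P(stop early) = P(X₁ ≤ 2). At p = 0.20 this is 0.0440 + 0.1539 + 0.2501 = 0.448.
- P(reject) = Σ over x = 3 to 14 of P(X₁ = x) · P(X₂ ≥ 8 − x). At p = 0.20 this is 0.0874; at p = 0.40 it is 0.8024.
- An exhaustive search finds 24 to be the smallest total size meeting both constraints, with 2/14 giving the lowest expected size under the null at that total (19.5).
- Dropout: 24 / (1 − 0.20) = 30.

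The plan's figures reproduce.

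**3. Illustrate the effect of misclassification.** The documents give no rate of such subjects, so the inflation m is an assumption. The true rate is held at 0.20 and the same formulas are evaluated at p = 0.20 + m. Since 80% of subjects are true non-responders, m corresponds to a share m / 0.80 of them being scored as responders.

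| Assumed m | Share of non-responders | P(stop at 14) | P(reject) |
|---|---|---|---|
| 0 | 0 | 0.448 | 0.087 |
| +0.5 point | 0.6% | 0.430 | 0.098 |
| +1 point | 1.25% | 0.411 | 0.110 |
| +2 points | 2.5% | 0.376 | 0.135 |
| +5 points | 6.25% | 0.281 | 0.230 |

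The margin between the attained 0.087 and the stated 0.10 absorbs half a point of inflation but not a full point.

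**4. The one-subject margin.** At a true 20%, the chance of passing stage 1 and finishing on exactly 7 of 24 is 0.092. That is not the chance that the result flips, which also needs at least one of the 17 non-responders to be misclassified. If each is misclassified with assumed probability q, the joint chance is 0.092 × [1 − (1 − q)¹⁷]:

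- q = 1%: 0.092 × 0.157 = 0.014
- q = 2.5%: 0.092 × 0.350 = 0.032

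**The case against.** The strongest reply is that the protocol does bring blood blasts into response assessment: section 7.1.2 says so in the same paragraph that points to Appendix A, and an assessor who follows it has to look at them. That stands, and it limits the point. A reader might infer that the plan requires subjects with circulating blasts to be scored as responders, or ignores blood blasts altogether. The documents do not support that. They name the variable and omit the rule.

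Appendix A is also headed as following the IWG criteria, and section 2.1 cites a published source, whose full text might settle the matter. That text is not in the documents, so it can neither be relied on nor ruled out. What is certain is that the protocol's own table has no such condition.

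A reader might further infer that the trial's type I error is inflated to 0.135 or 0.230. Nothing supports those inflation rates. A misclassified subject must combine low marrow blasts, no EMD and persistent leukemic blasts in the blood and, for CR, also recovered counts and transfusion independence. At half a point the error rate stays within 0.10. Likewise, 0.09 is the chance of finishing on 7 of 24, not of a changed conclusion.

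Finally, it is not settled that CRp feeds the 14/24 rules. The synopsis objective includes it, "Determine the complete response (CR, CRi, and CRp, see Appendix A) rate to treatment with ciprofloxacin and etoposide at the MTD", as does section 7.1.2, while section 11.1 names only CR and CRi. The gap in the CR and CRi rows exists either way.

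**Conclusion.** The point holds as a gap between a stated response variable and the table that defines response. As Appendix A is written, a subject with leukemic blasts in the blood can be counted as a responder on the primary endpoint, and classification is left to the assessor. Its size cannot be estimated from the documents. Under the assumed inflations the chance of a false rejection runs from 0.098 (+0.5 point) to 0.230 (+5 points), against 0.087 with none, and it passes the stated 0.10 somewhere between +0.5 and +1 point. These figures assume a true rate of exactly 20% and misclassification that acts equally in both stages. The sample size, the stopping boundary and the rejection boundary are correct and need no change. Severity: should be fixed.

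**What to change.** Add to the CR, CRi and CRp rows of Appendix A: 'no circulating leukemic blasts on the CBC differential paired with the response marrow'. State which CBC is paired. This needs saying because the response marrow window is Day 28 ±2 days in Table 1 and ±7 days in section 7.2.1, so the marrow and the visit CBC can fall on different dates. Score the 14- and 24-subject rules on the amended table, for whichever categories count once section 11.1 (CR + CRi) has been reconciled with the synopsis and section 7.1.2 (CR, CRi and CRp).

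The cost is an edit to one table and its cross-references. The differentials are already collected, and no visit, sample or extra subject is needed. The downside is that the observed response rate may be slightly lower.

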4.2 Treatment Duration

Phase Ib subjects who developed a DLT with the first cycle will be taken off study at the Cycle 1 Day 28 visit.

For all others, treatment with ciprofloxacin and etoposide will be repeated in 28-day cycles until:

- In Cycle 2, if the treating physician decides that the subject has rapidly progressive disease despite treatment;
- Subject withdrawal of consent for continued participation in the study;
- Inter-current illness that prevents further administration of study treatment;
- Unacceptable toxicity attributed to study treatment with ciprofloxacin and etoposide;
- Completion of 2 cycles of therapy from Day 1, Cycle 1;
- Disease progression defined by >25% increase in marrow blasts ([Appendix A](#));
- If, in the opinion of the PI or treating physician, continuation in the study could be detrimental to the subject's well-being;
- Significant deviation from inclusion/exclusion criteria in the opinion of the PI;
- Lost to follow-up (discontinuation date will be recorded as the date of last contact with subject); and/or
- Termination of the study.

Subjects with an ANC < 500/ μ L at the Day 28 assessment will be treated unless the Day 28 bone marrow shows < 5% cellularity. In that event, treatment will be held and a CBC will be repeated weekly until Day 42. A bone marrow will be repeated no later than Day 42 for subjects who

have treatment held. In the event that the subject does not show bone marrow recovery with a cellularity > 5% by Day 42 of treatment, the subject will be withdrawn from the study.

Table 3. Dosing Modifications

Event	Action
Disease Progression	Stop Therapy
ANC > 500/ μ L, No progression	Resume Therapy
ANC < 500/ μ L, Cellularity > 5%, No progression	Resume Therapy

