4.4.2 Hematologic (Blood/Bone Marrow) Toxicity

Dose delays or dose modifications are not required for hematologic toxicities unless the disease assessment shows bone marrow hypoplasia (< 5% cellularity). It is assumed that any cytopenia at diagnosis is due to resistant AML.

Management of neutropenia, neutropenic fever, thrombocytopenia, anemia, or bleeding should follow standard guidelines within the institution.

In the absence of medical indications (surgery, bleeding) platelet transfusions should be given to maintain counts > 10,000/ μ L .

Erythropoietin, G-CSF, or GM-CSF may not be used during protocol treatment.

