 - BUN, creatinine, uric acid, total bilirubin, AST, ALT, alkaline phosphatase, LDH, sodium, potassium, calcium, magnesium, phosphorous, bicarbonate, chloride, glucose, albumin, and total protein.

Cycle 1 Day 28

The C1D28 visit may occur \pm 48 hours from the protocol-specified date. All subjects will have the following procedures:

- Document concomitant medications and transfusions;
- AE assessment;
- Physical exam;
- Vital signs, including blood pressure, pulse, respirations, and temperature;
- Weight;
- 12-lead electrocardiogram (ECG), including rhythm, heart rate, and PR, QRS, and QTc intervals;
- ECOG Performance Score;
- Hematology laboratory evaluations:
 - Complete blood count (CBC) including hemoglobin, hematocrit, white blood cell (WBC) absolute differential including circulating blasts, and platelet count;
- Blood chemistry laboratory evaluations:
 - BUN, creatinine, uric acid, total bilirubin, AST, ALT, alkaline phosphatase, LDH, sodium, potassium, calcium, magnesium, phosphorous, bicarbonate, chloride, glucose, albumin, and total protein;
- Bone marrow aspirate and/or biopsy for clinical classification (cellularity, blast assessment) and cytogenetic testing, ; and
- Serum or urine pregnancy test – if applicable for females of childbearing potential.

At C1 D28, the subject will have completed protocol-specified treatment for Cycle 1. For subjects in Phase Ib, DLT assessment will occur at this point.

Cycle 2/Days 1, 8, 15, and 22

All subjects will have the following procedures completed on the visit, unless otherwise specified:

- Document concomitant medications and transfusions;
- AE assessment;
- Physical exam;
- Vital signs, including blood pressure, pulse, respirations, and temperature;
- Weight;
- ECOG Performance Score;
- Hematology laboratory evaluations (unless performed in the 24 hours prior to visit):
 - Complete blood count (CBC) including hemoglobin, hematocrit, white blood cell (WBC) absolute differential including circulating blasts, and platelet count; and

- Blood chemistry laboratory evaluations (unless performed in the 24 hours prior to visit):
 - BUN, creatinine, uric acid, total bilirubin, AST, ALT, alkaline phosphatase, LDH, sodium, potassium, calcium, magnesium, phosphorous, bicarbonate, chloride, glucose, albumin, and total protein.

Cycle 2 /Day 28 (± 2) and EOT (± 7)

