11.1 Determinations of Sample Size

An estimate of 8-24 patients are to be enrolled to Phase Ib portion of the study accounting for a 25% drop-out rate. Precise sample size cannot be defined, as it is dependent on the observed toxicity rate in this phase.

Subjects will be enrolled in the Phase II portion of the study once the MTD has been determined. The primary intention is to determine the complete response rate (CR + CR_i, see [Appendix A](#)) of ciprofloxacin and etoposide given at the MTD to subjects with resistant AML, which is achieved at the end of any treating cycle. The CR rate for AML subjects receiving etoposide alone is approximately 20% (the null hypothesis). We expect that the combination of ciprofloxacin and etoposide will improve the CR rate to 40%. In order to detect this difference with a type I error rate of 0.10 and power of 80%, when the true response rate is 40%, a minimum of 24 subjects who are evaluable for response will need to be accrued, based on the Simon's two-stage Minimax design. Specifically, in the first stage, we will enroll 14 evaluable subjects to this phase. The accrual will be temporarily suspended once the 14th evaluable subject is enrolled, pending response evaluation. If 2 or fewer respond, in these 14 subjects, the study will be stopped. Otherwise, continue to accrue additional 10 evaluable subjects (for a total of 24 evaluable subjects). The null hypothesis of 20% CR will be rejected if 8 or more CRs are observed in 24 subjects. Assuming 20% drop out rate, the total number of subjects to be enrolled to the Phase II portion is 30

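### Appendix A sets no marrow-cellularity condition for CRi or CRp, so an aplastic Day 28 marrow with low counts can be scored as a primary-endpoint response

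*Combined protocol and SAP*

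**What the plan says.** **Endpoint.** The synopsis states the Phase II objective as "Determine the complete response (CR, CRi, and CRp, see Appendix A) rate", and Section 7.1.2 agrees: "The efficacy outcomes of interest will be CR (including CRi and CRp"). Section 11.1 names CR and CRi, and counts a response "which is achieved at the end of any treating cycle". Section 2.1 names only CR but also refers to Appendix A.

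**Definition.** Appendix A tabulates neutrophils, platelets, marrow blasts and one further column. Full CR needs neutrophils >1,000, platelets >100,000, blasts <5% and "Transfusion independent, no evidence of EMD". The row "CRi (CR with incomplete blood counts") needs neutrophils <1,000, platelets <100,000, blasts <5% and no EMD (extramedullary disease). CRp differs from CRi in requiring neutrophils >1,000. No row mentions cellularity.

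**Marrow recovery.** Section 4.2 holds treatment when ANC is <500 at Day 28 and the marrow has <5% cellularity. It requires a repeat marrow no later than Day 42. Its withdrawal clause begins "In the event that the subject does not show bone marrow recovery with a cellularity > 5% by Day 42 of treatment". Section 4.4.2 uses the same threshold: no delay or modification is required for hematologic toxicity "unless the disease assessment shows bone marrow hypoplasia (< 5% cellularity").

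**Data collected.** The Day 28 visit in Section 6.2 includes "Bone marrow aspirate and/or biopsy for clinical classification (cellularity, blast assessment) and cytogenetic testing". Cellularity is thus read at each Day 28 marrow but plays no part in the response table.

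**The concern.** A marrow with almost no cells can show <5% blasts because leukemia has cleared, or because the drugs have emptied the marrow and the disease has yet to return. Blast percentage and low counts alone do not separate the two. Appendix A asks for nothing else apart from absence of EMD, so both are scored CRi.

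The protocol foresees such marrows, since Sections 4.2 and 4.4.2 write rules for them. Section 1.2 reports myelosuppression as the major toxicity of oral etoposide. The subject stays in the denominator: Section 4.1 makes Phase II subjects evaluable for response after one cycle given per protocol, and Section 11.2.3 adds only one post-dose efficacy assessment.

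At stake are both Phase II decisions: stop at 2 or fewer responders of 14, and reject the 20% null at 8 or more of 24. Any misclassification of this kind pushes toward continuing and toward declaring activity.

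**Working it through.** **Inputs (Section 11.1).** p0 = 0.20, p1 = 0.40, type I error 0.10, power 80%; n1 = 14, stop if ≤2; n = 24, reject if ≥8.

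**1. The plan's own design.** With X1 ~ Bin(14, p) and X2 ~ Bin(10, p):

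- P(stop) = P(X1 ≤ 2)
- P(success) = Σ over x = 3 to 14 of P(X1 = x) × P(X2 ≥ 8 − x)

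At p = 0.20, P(stop) = 0.0440 + 0.1539 + 0.2501 = 0.448. The terms of P(success) are:

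- x = 3: 0.2501 × 0.0328 = 0.0082
- x = 4: 0.1720 × 0.1209 = 0.0208
- x = 5: 0.0860 × 0.3222 = 0.0277
- x = 6: 0.0322 × 0.6242 = 0.0201
- x = 7: 0.0092 × 0.8926 = 0.0082
- x ≥ 8: 0.0024

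The sum is 0.0874. At p = 0.40, P(success) = 0.802. The stated design therefore reproduces, with type I error inside 0.10 and power just above 80%. An exhaustive minimax search returns the same 14/2 and 24/7 boundaries.

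**2. One subject against the two rules.** Take a Day 28 marrow with <5% cellularity and <5% blasts, ANC <500, platelets <100,000 and no EMD.

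| Rule | Result |
|---|---|
| Appendix A, CRi | All four conditions met: response |
| Section 4.2 | Treatment held; marrow repeated by Day 42; withdrawn if cellularity has not recovered |

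No text says whether the Day 28 or the repeat marrow decides response.

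**3. Effect on the decision rule.** Assumption: a fraction q of subjects who are not true responders is scored CRi or CRp on such a marrow. The documents do not give q. At a true rate of 20% the scored rate is p = 0.20 + 0.80q. Putting p into the formulas of step 1:

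| q | Scored rate p | P(success) | P(stage 1 stop) | Expected misclassified of 24 (24 × 0.80 × q) |
|---|---|---|---|---|
| 0 | 0.200 | 0.087 | 0.448 | 0 |
| 1% | 0.208 | 0.105 | 0.419 | 0.19 |
| 2% | 0.216 | 0.125 | 0.390 | 0.38 |
| 5% | 0.240 | 0.196 | 0.311 | 0.96 |
| 10% | 0.280 | 0.346 | 0.203 | 1.92 |

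At q = 1% the error is already slightly above 0.10. At q = 5%, about one misclassified subject in 24, it is more than double the design value (0.196 / 0.087 = 2.25).

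**The case against.** **The table may be only a summary.** Its title refers to the IWG criteria, and Section 2.1 cites their source. Investigators who know the full criteria might not score an aplastic marrow. That may happen in practice, but the synopsis and Sections 2.1, 7.1.2 and 11.1 all send the reader to Appendix A, and no text in the protocol adds a condition. The written rule remains open.

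**The scoring marrow is not fixed at Day 28.** Section 7.2.1 allows ±7 days and Section 4.2 orders a repeat for held subjects, so a site could wait for the repeat. This stands in part. It shows that the deciding marrow is unstated, which is itself something to settle.

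**Section 4.2 governs treatment, not response.** This stands. A reader might infer that withdrawal for failed marrow recovery contradicts a CRi. It does not: a subject can respond and still stop treatment. What Section 4.2 shows is that the protocol already regards such a marrow, with ANC <500, as unrecovered.

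**An empty marrow does not count on its own.** Also true. The count, blast and EMD conditions must be met as well, and the Section 4.2 hold needs ANC <500.

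**The size is hypothetical.** This stands. At q of 1% or 2% the effect is modest, and q must exclude subjects whose aplasia resolves into real remission. Section 3.2.1 chose a 7-day etoposide course because 14 days was too toxic, so rates from harsher schedules cannot be carried over.

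**Conclusion.** The gap is real and lies in the primary endpoint: as written, Appendix A can score marrow aplasia with low counts as CRi. CRp lacks a cellularity condition too, though it requires neutrophils >1,000. The bias runs one way, toward success, and affects both the stage 1 and the final rule.

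Its size is not known. The range from 0.105 to 0.346 for q between 1% and 10% rests on an assumed q. It also takes the 20% null to be a rate of true remission, which the documents do not spell out.

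Three stronger conclusions are tempting but unsupported. A reader might infer that the trial would be declared active because it is myelosuppressive; without a value for q, only the possibility is shown. A reader might infer that every empty Day 28 marrow is a responder; the other conditions prevent that. And a reader might infer that response duration would run from a remission that never existed; the documents define no start date for duration.

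**What to change.** Change endpoint scoring only; the treatment, hold and withdrawal rules stay as they are. State in Appendix A and Section 11.1:

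1. CR, CRi and CRp are not scored on a marrow with <5% cellularity, the protocol's own hypoplasia threshold.
2. For subjects held under Section 4.2, response is taken from the repeat marrow due by Day 42. Those whose cellularity has not recovered by then are non-responders.
3. For other subjects with a <5% cellularity marrow (ANC of 500 or more, or after Cycle 2), no repeat is scheduled. Score from the next marrow actually obtained. If there is none, classify the subject as not a confirmed response in the primary analysis, and report a sensitivity analysis counting such subjects as responders.

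The cost is a few sentences of amendment. Cellularity is already read on each Day 28 marrow, and no new procedure is needed. The observed CR rate may be lower, some responses will be scored later, and a few genuine responders without a repeat marrow may be missed in the primary count. The sensitivity analysis in item 3 shows how much that last group matters.
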